#### Dosing

• Study treatment administration.

#### After dosing, the following procedures will be completed:

- Vital signs: Supine blood pressure, pulse rate, respiratory rate, and oral temperature after completion of infusion. Infusion site reaction monitoring.
- AE monitoring.
- Concomitant medication monitoring.
- 6.7. Active Treatment: Visit 7 (Day 113±3) and for Cohort 1, Visit 15 (Day 337±3)
  - **Pregnancy Test**: A highly sensitive urine pregnancy test will be performed on all female subjects
  - Diary Cards: For collection of first day of each menstrual cycle for WOCBP.
  - Contraception Review: Confirmation of use of acceptable forms of contraception
  - Weight
  - Vital Signs: Supine blood pressure, pulse rate, respiratory rate, and oral temperature.
  - Clinical laboratory testing:
    - Hematology with complete blood count and differential, comprehensive metabolic panel (sodium, potassium, chloride, carbon dioxide, blood urea nitrogen, creatinine, calcium, glucose, total protein, albumin, total bilirubin, AST, ALT, alkaline phosphatase) gamma-glutamyl transferase (GGT), prothrombin time (PT), activated partial thromboplastin time (aPTT), creatine kinase, amylase, cardiac troponin I. Urinalysis.
  - Serum ferritin, serum iron, % transferrin saturation, TIBC: fasting blood collection
  - GLDH
  - **Fecal Occult Blood:** Fecal sample is to be collected at home within 1 week prior to scheduled visit.
  - C-SSRS
  - PK/PD sample: predose

- **Biomarker collection:** Blood will be collected for proteomic, metabolomic, and genomic biomarker analysis
- **Functional assessments:** Must be conducted in the following order: Respiratory function (FVC, FEV1, MIP, MEP), 4SC, 2MWT, 10-meter walk/run, TUG, strength assessment (MMT, hand-held dynamometry) and PUL.

## Dosing

• Study treatment administration.

### After dosing, the following procedures will be completed:

- Vital signs: Supine blood pressure, pulse rate, respiratory rate, and oral temperature after completion of infusion.PK/PD sample collection: Collected at end of infusion (hour 2)
- Infusion site reaction monitoring.
- AE monitoring.
- Concomitant medication monitoring.

# 6.8. Follow up: For Cohort 1, Visit 19 (Day 449±3) and for Cohort 2 and 3, Visit 11 (Day 225±3)

This visit will occur over 2 days.

- Physical Examination, including Nose and Throat Mucosal Exam.
- **Pregnancy Test**: A highly sensitive urine pregnancy test will be performed on all female subjects
- **Diary Cards:** For collection of first day of each menstrual cycle for WOCBP.
- Contraception Review: Confirmation of use of acceptable forms of contraception
- Weight
- Vital Signs: Supine blood pressure, pulse rate, respiratory rate, and oral temperature.
- 12-lead ECG: ECGs will be performed in triplicate
- Echocardiogram
- Clinical laboratory testing:

- Hematology with complete blood count and differential, comprehensive metabolic panel (sodium, potassium, chloride, carbon dioxide, blood urea nitrogen, creatinine, calcium, glucose, total protein, albumin, total bilirubin, AST, ALT, alkaline phosphatase) gamma-glutamyl transferase (GGT), prothrombin time (PT), activated partial thromboplastin time (aPTT), creatine kinase, amylase, cardiac troponin I. Urinalysis.
- Serum ferritin, serum iron, % transferrin saturation, TIBC: fasting blood collection
- Horomone Testing: LH, FSH, estrogen in WOCBP
- GLDH
- Fecal Occult Blood: Fecal sample is to be collected at home within 1 week prior to scheduled visit.
- C-SSRS
- **MRI-liver**: Liver MRI will be obtained for iron accumulation
- **MRI-muscle:** WB-MRI and dedicated thigh MRI will be performed for muscle quantity and quality
- **DXA Whole Body:** Whole body DXA will be performed for lean body mass assessment.
- **DXA Spine and Hip:** Spine and hip DXA will be performed for BMD.
- **Functional assessments:** Must be conducted in the following order: Respiratory function (FVC, FEV1, MIP, MEP), 4SC, 2MWT, 10-meter walk/run, TUG, strength assessment (MMT, hand-held dynamometry) and PUL.
- **Needle muscle biopsy:** Following WB-MRI and functional assessments, a needle muscle biopsy of the tibialis muscle will be performed.
- Quality of Life assessments
  - InQol
  - SF-36
- Immunogenicity sample collection.
- PD sample collection
- PK sample collection

- Adverse Event monitoring
- Infusion site reaction monitoring
- Concomitant medication

6.9. Follow-up: For Cohort 1, Visit 20 (Day 561±3) and for Cohort 2 and 3 Visit 12 (Day 337±3)

- Physical Examination, including Nose and Throat Mucosal Exam.
- **Pregnancy Test**: A highly sensitive urine pregnancy test will be performed on all female subjects
- Diary Cards: For collection of first day of each menstrual cycle for WOCBP.
- Contraception Review: Confirmation of use of acceptable forms of contraception
- Weight
- Vital Signs: Supine blood pressure, pulse rate, respiratory rate, and oral temperature.
- **12-lead ECG:** ECGs will be performed in triplicate
- Echocardiogram
- Clinical laboratory testing:
  - Hematology with complete blood count and differential, comprehensive metabolic panel (sodium, potassium, chloride, carbon dioxide, blood urea nitrogen, creatinine, calcium, glucose, total protein, albumin, total bilirubin, AST, ALT, alkaline phosphatase) gamma-glutamyl transferase (GGT), prothrombin time (PT), activated partial thromboplastin time (aPTT), creatine kinase, amylase, cardiac troponin I. Urinalysis.
- Serum ferritin, serum iron, % transferrin saturation, TIBC: fasting blood collection
- Horomone Testing: LH, FSH, estrogen in WOCBP
- GLDH
- **Fecal Occult Blood:** Fecal sample is to be collected at home within 1 week prior to scheduled visit.
- C-SSRS
- **MRI-liver**: Liver MRI will be obtained for iron accumulation

- **MRI-muscle:** WB-MRI and dedicated thigh MRI will be performed for muscle quantity and quality
- **DXA Whole Body:** Whole body DXA will be performed for lean body mass assessment.
- **DXA Spine and Hip:** Spine and hip DXA will be performed for BMD.
- **Functional assessments:** Must be conducted in the following order: Respiratory function (FVC, FEV1, MIP, MEP), 4SC, 2MWT, 10-meter walk/run, TUG, strength assessment (MMT, hand-held dynamometry) and PUL.
- **Needle muscle biopsy:** Following WB-MRI and functional assessments, a needle muscle biopsy of the tibialis muscle will be performed.
- Quality of Life assessments
  - InQol
  - SF-36
- **Immunogenicity** sample collection.
- PK sample collection
- PD sample collection
- Adverse Event monitoring
- Concomitant medication

# 6.10. Extension Period: For Cohort 1 (Visits 21,22,23,25, and 26), for Cohort 2 (Visits 13,14,15,17,18,20,21), for Cohort 3 (Visits 13,14, 16, 17)

- **Pregnancy Test**: A highly sensitive urine pregnancy test will be performed on all female subjects
- Diary Cards: For collection of first day of each menstrual cycle for WOCBP.
- Contraception Review: Confirmation of use of acceptable forms of contraception
- Weight
- **Dosing**: study treatment administration
- Infusion site reaction monitoring.
- AE monitoring.

• Concomitant medication monitoring.

6.11. Extension Period: For Cohort 1 (Visit 24), for Cohort 2 (Visits 16 and 19), and for Cohort 3 (Visit 15)

- Physical Examination, including Nose and Throat Mucosal Exam
- **Pregnancy Test**: A highly sensitive urine pregnancy test will be performed on all female subjects
- Diary Cards: For collection of first day of each menstrual cycle for WOCBP.
- Contraception Review: Confirmation of use of acceptable forms of contraception
- Weight
- Vital signs: Supine blood pressure, pulse rate, respiratory rate, and oral temperature.
- **12-lead ECG:** ECGs will be performed in triplicate (only in Cohort 2- Visit 19)
- Clinical laboratory testing:
  - Hematology with complete blood count and differential, comprehensive metabolic panel (sodium, potassium, chloride, carbon dioxide, blood urea nitrogen, creatinine, calcium, glucose, total protein, albumin, total bilirubin, AST, ALT, alkaline phosphatase) gamma-glutamyl transferase (GGT), prothrombin time (PT), activated partial thromboplastin time (aPTT), creatine kinase, amylase, cardiac troponin I. Urinalysis.
- Serum ferritin, serum iron, % transferrin saturation, TIBC: fasting blood collection
- GLDH
- **Fecal Occult Blood:** Fecal sample is to be collected at home within 1 week prior to scheduled visit.
- C-SSRS
- Functional assessments: Must be conducted in the following order: Respiratory function (FVC, FEV1, MIP, MEP), 4SC, 2MWT, 10-meter walk/run, TUG, strength assessment (MMT, hand-held dynamometry) and PUL.
- **Dosing**: study treatment administration
- Infusion site reaction monitoring.
- AE monitoring.

• Concomitant medication monitoring.

6.12. Extension Period: For Cohort 1 (Visit 27), for Cohort 2 (Visit 22), and for Cohort 3 (Visit 18)

- Physical Examination, including Nose and Throat Mucosal Exam
- **Pregnancy Test**: A highly sensitive urine pregnancy test will be performed on all female subjects
- Diary Cards: For collection of first day of each menstrual cycle for WOCBP.
- Contraception Review: Confirmation of use of acceptable forms of contraception
- Weight
- Height
- Vital signs: Supine blood pressure, pulse rate, respiratory rate, and oral temperature.
- **12-lead ECG:** ECGs will be performed in triplicate
- Echocardiogram
- Clinical laboratory testing:
  - Hematology with complete blood count and differential, comprehensive metabolic panel (sodium, potassium, chloride, carbon dioxide, blood urea nitrogen, creatinine, calcium, glucose, total protein, albumin, total bilirubin, AST, ALT, alkaline phosphatase) gamma-glutamyl transferase (GGT), prothrombin time (PT), activated partial thromboplastin time (aPTT), creatine kinase, amylase, cardiac troponin I. Urinalysis.
- Serum ferritin, serum iron, % transferrin saturation, TIBC: fasting blood collection
- Horomone Testing: LH, FSH, estrogen in WOCBP
- GLDH
- **Fecal Occult Blood:** Fecal sample is to be collected at home within 1 week prior to scheduled visit.
- C-SSRS
- **MRI-liver**: Liver MRI will be obtained for iron accumulation
- **DXA Spine and Hip:** Spine and hip DXA will be performed for BMD.

- **Functional assessments:** Must be conducted in the following order: Respiratory function (FVC, FEV1, MIP, MEP), 4SC, 2MWT, 10-meter walk/run, TUG, strength assessment (MMT, hand-held dynamometry) and PUL.
- Quality of Life assessments
  - InQol
  - SF-36
- **Dosing**: study treatment administration
- Immunogenicity sample collection.
- PK sample collection
- PD sample collection
- **Biomarker collection:** Blood will be collected for proteomic, metabolomic, and genomic biomarker analysis
- Infusion site reaction monitoring.
- AE monitoring.
- Concomitant medication monitoring.
- 6.13. Telephone Follow-up: 30 +/-3days after final dosing visit
  - AE monitoring.
  - Concomitant medication

## 6.14. Unscheduled Visits

Subjects may return for unscheduled visits as determined by the investigator or the sponsor to complete unscheduled safety assessments. These assessments may include:

- Fecal occult blood.
- C-SSRS
- Weight.
- Physical Examination, including Nose and Throat Mucosal Exam.
- Vital Signs: Supine blood pressure, pulse rate, respiratory rate, and oral temperature.
- 12 lead ECG.

- Echocardiogram
- Clinical laboratory testing:
  - Hematology with complete blood count and differential, comprehensive metabolic panel (sodium, potassium, chloride, carbon dioxide, blood urea nitrogen, creatinine, calcium, glucose, total protein, albumin, total bilirubin, AST, ALT, alkaline phosphatase) gamma-glutamyl transferase (GGT), prothrombin time (PT), activated partial thromboplastin time (aPTT), creatine kinase, amylase, cardiac troponin I. Urinalysis.
- Horomone Testing: LH, FSH, estrogen in WOCBP
- **Preganancy test:** A highly sensitive urine pregnancy test will be performed on all female subjects
- PK sample collection.
- PD sample collection.
- MRI-liver: Liver MRI will be obtained for iron accumulation
- **MRI-muscle:** WB-MRI and dedicated thigh MRI will be performed for muscle quantity and quality
- **DXA Whole Body:** Whole body DXA will be performed for lean body mass assessment.
- **DXA Spine and Hip:** Spine and hip DXA will be performed for BMD.
- Infusion site reaction monitoring.
- Adverse event (AE) monitoring.
- Concomitant medication monitoring.

#### 6.15. Subject Withdrawal

Subjects who request to discontinue study treatment will remain in the study and must continue to be followed for protocol specified follow-up procedures. The only exception to this is when a subject specifically withdraws consent for any further contact with him/her. The subject should notify the investigator of the decision to withdraw consent from future follow-up in writing, whenever possible. The withdrawal of consent should be explained in detail in the medical records by the investigator, as to whether the withdrawal is from further treatment with study drug only or also from study procedures and/or post treatment study follow-up, and entered on the appropriate CRF page. In the event that vital status (whether the subject is alive or dead) is being measured, publicly available information should be used to determine vital status only as appropriately directed in accordance with local law.

If the subject withdraws from the study and also withdraws consent for disclosure of future information, no further evaluations should be performed and no additional data should be collected. The sponsor may retain and continue to use any data collected before such withdrawal of consent.

Subjects may withdraw from the study at any time at their own request, or they may be withdrawn at any time at the discretion of the investigator or sponsor for safety or behavioral reasons, or the inability of the subject to comply with the protocol-required schedule of study visits or procedures at a given study site.

If a subject does not return for a scheduled visit, every effort should be made to contact the subject. All attempts to contact the subject and information received during contact attempts must be documented in the subject's medical record. In any circumstance, every effort should be made to document subject outcome, if possible. The investigator should inquire about the reason for withdrawal, request that the subject return for a final visit, if applicable, and follow-up with the subject regarding any unresolved AEs.

It may be appropriate for the subject to return to the clinic for final safety assessments and to be questioned regarding their reason for withdrawal. The following assessments may be performed according to the Schedule of Activities:

Assessments in the Early Withdrawal visit may include:

- Physical Examination, including Nose and Throat Mucosal Exam.
- **Pregnancy Test**: A highly sensitive urine pregnancy test will be performed on all female subjects
- **Diary Card:** For collection of first day of each menstrual cycle for WOCBP.
- Contraception Review: Confirmation of use of acceptable forms of contraception
- Vital signs: Supine blood pressure, pulse rate, respiratory rate, and oral temperature.
- 12-lead ECG: ECGs will be performed in triplicate
- Echocardiogram
- Clinical laboratory testing:
  - Hematology with complete blood count and differential, comprehensive metabolic panel (sodium, potassium, chloride, carbon dioxide, blood urea nitrogen, creatinine, calcium, glucose, total protein, albumin, total bilirubin, AST, ALT, alkaline phosphatase) gamma-glutamyl transferase (GGT), prothrombin time (PT), activated partial thromboplastin time (aPTT), creatine kinase, amylase, cardiac troponin I. Urinalysis.

- Serum ferritin, serum iron, % transferrin saturation, TIBC: fasting blood collection
- Horomone Testing: LH, FSH, estrogen in WOCBP
- GLDH
- **Fecal Occult Blood:** Fecal sample is to be collected at home within 1 week prior to scheduled visit.
- C-SSRS
- **MRI-liver**: Liver MRI will be obtained for iron accumulation
- **MRI-muscle:** WB-MRI and dedicated thigh MRI will be performed for muscle quantity and quality
- **DXA Whole Body:** Whole body DXA will be performed for lean body mass assessment.
- **DXA Spine and Hip:** Spine and hip DXA will be performed for BMD.
- **Functional assessments:** Must be conducted in the following order: Respiratory function (FVC, FEV1, MIP, MEP), 4SC, 2MWT, 10-meter walk/run, TUG, strength assessment (MMT, hand-held dynamometry), and PUL.
- **Needle muscle biopsy:** Following WB-MRI and functional assessments, a needle muscle biopsy of the tibialis muscle will be performed.
- Quality of Life assessments
  - InQol
  - SF-36
- Immunogenicity sample collection.
- PD sample collection
- PK sample collection
- Adverse Event monitoring
- Infusion site reaction
- Concomitant medication

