# **SCHEDULE OF ACTIVITIES**

## Table 1 Cohort 1

	Screen	Lead- In		w-up	Early With- drawal								
				_		A (:	5 mg/kg	g)			19 (449 ±3)	20 (561 ±3)	
Visit Number (Study Day Visit	1 (-125	2 (-111	3 (1)	4 (29 ±3)	5 (57 ±3)	6 (85 ±3)	7 (113 ±3)	8 (141 ±3)	9 (169 ±3)	10 (197 ±3)			
Window) a	to -112)	to - 110)				B (4	0 mg/kg	g)					
		110)	11 (225 ±3)	12 (25 3 ±3)	13 (28 1 ± 3)	14 (30 9 ±3)	15 (337 ±3)	16 (365 ±3)	17 (393 ±3)	18 (421 ±3)			
Entry/Safety Assessme	ents	 		±3)	- 3)	 )							
Informed Consent	X												
Demography	Х												
Medical History b	X												
Medication History	X												
Inclusion/Exclusion	X												
Enrollment c	X												
Physical Examination	X	X	Х			X					X	X	Х
Pregnancy Test d	X	Х	X	Х	X	X	X	Х	X	Х	Х	Х	Х
Diary Cards d	X	X	X	Х	X	X	Х	Х	X	Х	X	X	Х
Contraception Review	X	X	X	Х	X	X	Х	Х	Х	Х	Х	Х	Х
Height		Х											
Weight e	Х	Х	X	Х	X	X	Х	X	X	Х	X	X	Х
Vital Signs f	Х	Х	Х	Х	X	X	Х	Х	Х	Х	Х	Х	Х

	Screen	Lead- In				Tr	eatmen	t			Follo	w-up	Early With- drawal
						A (:	5 mg/kg	g)			19 (449 ±3)	20 (561 ±3)	
Visit Number (Study Day Visit	1 (-125	2 (-111	3 (1)	4 (29 ±3)	5 (57 ±3)	6 (85 ±3)	7 (113 ±3)	8 (141 ±3)	9 (169 ±3)	10 (197 ±3)			
Window) a	to -112)	to - 110)				B (4	0 mg/kg	g)					
		110)	11 (225 ±3)	12 (25 3 ±3)	13 (28 1± 3)	14 (30 9 ±3)	15 (337 ±3)	16 (365 ±3)	17 (393 ±3)	18 (421 ±3)			
12- lead ECG	Х		Х		, í	X					X	Х	Х
Echocardiogram	Х										X	Х	Х
Clinical Laboratory Tests g	Х		X	Х	X	X	Х	Х	X	Х	Х	Х	Х
Serum Ferritin, Serum Iron, Transferrin Saturation, TIBC	Х		X	X	X	X	Х	X	X	Х	X	х	Х
Hormone Testing (LH, FSH, estrogen) h	Х	X	X	Х	X	X	Х	Х	X	Х	X	Х	Х
GLDH	X	X	X	Х	X	X	Х	X	X	Х	X	Х	Х
Fecal Occult Blood i	Х		Х	Х	X	X	Х	X	X	Х	X	Х	Х
C-SSRS	Х	X	X	Х	X	X	Х	X	X	Х	X	Х	Х
Imaging Assessments													
MRI-Liver	X		Xº			X					X	X	Х
MRI-Muscle j		Х	Х								Х	X	Х
DXA Whole Body		X	Х								X	X	Х
DXA Spine and Hip			X								X	X	X
Functional Assessmen	ts												
Muscle Strength		X	X				X				X	X	Х

	Screen	Lead- In	Treatment									w-up	Early With- drawal
						Δ (	5 mg/kg	ı)			19 (449 ±3)	20 (561 ±3)	
Visit Number (Study Day Visit	1 (-125	2 (-111	3 (1)	4 (29 ±3)	5 (57 ±3)	$     \begin{array}{c}       6 \\       (85 \\       \pm 3)     \end{array} $	$\frac{5 \text{ mg/ kg}}{7}$ (113 ±3)	8 (141 ±3)	9 (169 ±3)	10 (197 ±3)		)	

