## SCHEDULE OF ACTIVITIES

#### Table 2 Cohort 2 and 3

	G	Lead-				T							Early
	Screen	in	-		-		eatment	-		10	Follo		Withdrawal
Visit Number (Study Day Visit Window) a	1 (-125 to -112)	2 (-111 to -110)	3 (1)	4 (29 ± 3)	5 (57 ±3)	6 (85 ±3)	7 (113 ±3)	8 (141 ±3)	9 (169 ±3)	10 (197 ±3)	11 (225 ±3)	12 (337 ±3)	
Entry/Safety Assessments													
Informed Consent	X												
Demography	X												
Medical History b	Х												
Medication History	X												
Inclusion/Exclusion	Х												
Enrollment c	Х												
Physical Examination	Х	X	Х			Х					Х	X	Х
Pregnancy Test d	Х	X	Х	X	Х	X	X	X	X	X	X	X	Х
Diary Cards d	Х	X	Х	Х	X	Х	X	X	X	Х	Х	X	Х
Contraception Review	Х	Х	X	X	X	X	X	X	X	X	X	X	Х
Height		X											
Weight e	Х	Х	X	X	X	X	X	X	X	X	Х	Х	Х
Vital Signs f	Х	Х	Х	X	X	Х	X	X	X	Х	Х	Х	Х
12- lead ECG	X		Х			X					X	X	Х
Echocardiogram	X										X	X	
Clinical Laboratory Tests g	Х		Х	Х	X	Х	Х	X	X	X	Х	X	Х
Serum Ferritin, Serum Iron, Transferrin Saturation, TIBC	X		X	X	X	X	X	X	X	X	Х	X	Х
Hormone Testing (LH, FSH, estrogen) h	X	X	X	X	X	Х	X	X	X	Х	Х	X	Х

	Screen	Lead- in				Tre	eatment	ł			Follov	v-un	Early Withdrawal
Visit Number (Study Day Visit Window) a	1 (-125 to -112)	2 (-111 to -110)	3 (1)	4 (29 ± 3)	5 (57 ±3)	6 (85 ±3)	7 (113 ±3)	8 (141 ±3)	9 (169 ±3)	10 (197 ±3)	11 (225 ±3)	12 (337 ±3)	
GLDH	X	X	X	X	X	Х	Х	X	X	Х	Х	Х	Х
Fecal Occult Blood i	X		X	X	X	Х	X	X	X	Х	Х	Х	Х
C-SSRS	Х	Х	Х	Х	Х	Х	Х	X	X	Х	Х	Х	Х
Imaging Assessments													
MRI-Liver	X					Х					Х	X	X
MRI-Muscle j		Х	X								Х	Х	Х
DXA Whole Body		Х	X								Х	Х	Х
DXA Spine and Hip			X								Х	Х	Х
Functional Assessments													
Muscle Strength (MMT, dynamometry)		X	X				X				Х	X	X
4SC		Х	X n				Х				Х	Х	Х
10-meter walk/run		Х	X n				Х				Х	Х	Х
2MWT		X	X n				Х				Х	Х	Х
Timed up-and-go		Х	X n				Х				Х	Х	Х
PUL		Х	X n				X				Х	Х	Х
InQol, SF-36			Х								Х	Х	Х
Respiratory Function (FVC, FEV1, MIP/MEP)		X	Х				X				Х	Х	Х
Study Treatment Administration													
Study Treatment Administration k			Х	Х	Х	Х	Х	X	X	Х			
PK/PD/Immunogenicity	1	1	1	1	1								
Needle muscle biopsy		X	X								X	Х	Х
Immunogenicity			X								X	Х	Х
PD sample		X	X		X		X		X		Х	Х	Х
PK samples 			Х		Х		Х		Х		Х	Х	Х

	Screen	Lead- in		Treatment Follow									Early Withdrawal

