## 1.12.4. Cardiac

Based on recent literature on the biology of GDF-8 and GDF-11 in modulation of cardiomyocyte and cardiac function and the potential for cardiac dysfunction in the target population of LGMD2I subjects, it is appropriate to focus on the potential for an interaction. In monkey toxicity studies up to 26 weeks, no abnormality of cardiac function or histology was observed. In rats dosed with  $\geq$ 150 mg/kg/week for 26 weeks, a reduction in heart weight was noted, but there were no microscopic findings. In light of the hypothetical risk of an effect of PF-06252616 on cardiac muscle development or function, monitoring with 12-lead ECG for rhythm or morphological change by echocardiography to evaluate left ventricular ejection fraction (LVEF) and left ventricular end systolic volume (LVESV) and cardiac Troponin I for cardiac muscle tissue injury will be performed. Additional cardiac parameters (eg, cardiac strain) may be collected by echocardiogram for exploratory analyses. Abnormal values for each of these measures have been reported in LGMD2I . In light of the variability of findings in disease, no pre-specified stopping rules have been defined.

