# In the extension period, all the tests and procedures listed in the early withdrawal visit will be completed except for MRI- muscle, DXA of the whole body, and needle muscle biopsy.

In the event of clinically important treatment-emergent suicidal ideation or suicidal behavior, the subject will be withdrawn from the study and will receive the appropriate medical care. The Investigator will follow up until the subject's condition has stabilized. Additionally, a risk assessment or evaluation of suicide risk will be completed by a mental health provider as part of the psychiatric evaluation and assessment of subject safety. Refer to Section7, Assessments. Clinically important suicidality includes but is not limited to:

- Suicidal behavior (with or without intent of suicide or serious self-harm).
- Determination of "yes" on question 4 (Active Suicidal Ideation with Some Intent or Act, Without Specific Plan) for the Suicidal Ideation section of the C-SSRS.
- Determination of "yes" on question 5 (Active Suicidal Ideation with Specific Plan and Intent) for the Suicidal Ideation section of the C-SSRS.
- Determination of "yes" on the question of Actual Attempt, Interrupted Attempt, Aborted Attempt, or Preparatory Acts or Behavior for Suicidal Behavior section of C-SSRS.
- Acute suicidality to such a degree that precaution against suicide must be exercised.

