#### 7.1.5. Echocardiogram

Echocardiograms should be collected at times specified in the Schedule of Activities section of this protocol. To ensure safety of the subjects, a qualified individual at the investigator site will evaluate the echocardiogram for ejection fraction (EF) and left ventricular end systolic volume (LVESV).

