#### 7.10. Triggered Requirements

Condition/ Criteria	Action
Moderate Iron overload/ If the liver iron content	The subject should be referred to a hepatologist for
estimate as determined by R2* value is above the "mild	further assessment
overload" range (R2* >369 Hz at 3.0 T	
Cardiomyopathy/ If the LVEF falls 10% of baseline on	The subject should be referred to a cardiologist for
the cardiac echocardiogram at any follow-up visit	further assessment.

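### Schedule of Activities Table 2 (Cohorts 2 and 3) leaves the Early Withdrawal echocardiogram unmarked, although Section 6.15 lists the test for that visit

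*Protocol*

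**What the plan says.** Section 6.15 introduces the Early Withdrawal visit with "The following assessments may be performed according to the Schedule of Activities". The list that follows includes "Echocardiogram" and sets no cohort limit. Section 7.1.5 also leaves timing to the tables: "Echocardiograms should be collected at times specified in the Schedule of Activities section of this protocol".

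The tables differ. The schedule headed "Table 1 Cohort 1" marks the echocardiogram in its Early Withdrawal column. The one headed "Table 2 Cohort 2 and 3" marks it at Screening, Visit 11 and Visit 12 and leaves Early Withdrawal empty. Extension Tables 3.1, 3.2 and 3.3 each mark it at early withdrawal or termination. For withdrawals during the extension, Section 6.15 states that "all the tests and procedures listed in the early withdrawal visit will be completed except for MRI- muscle, DXA of the whole body" and the needle biopsy. The echocardiogram is not among those exceptions.

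The measurement has a defined role. Section 2.2.1 includes LVEF by echocardiogram in the primary safety endpoint. Section 1.12.4 sets out cardiac monitoring "In light of the hypothetical risk of an effect of PF-06252616 on cardiac muscle development or function", with echocardiographic LVEF and LVESV as one part of it. The cardiac entry in Section 7.10 begins "Cardiomyopathy/ If the LVEF falls 10% of baseline on" a follow-up echocardiogram, and its action is referral to a cardiologist. SAP Section 8.2.1.4 plans summaries of absolute and percentage change in LVEF and LVESV, with LVEF shift tables by cohort and overall.

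**The concern.** Text and table disagree, and the text gives way to the table. A coordinator working from Table 2 would book the ECG, laboratory tests, liver and muscle MRI, DXA and muscle biopsy for an Early Withdrawal visit, but not the echocardiogram.

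The blank matters because Cohorts 2 and 3 have no other post-dose echocardiogram until dosing is over. Early leavers may also include people withdrawn for safety reasons, or withdrawn as Section 6.15 requires for C-SSRS findings. For them the final visit is the last planned chance to measure left ventricular function. Without it, only the screening value exists. The Section 7.10 comparison is then not scheduled, and the subject has no scheduled post-baseline value for the SAP's LVEF and LVESV summaries.

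**Working it through.** The plan states no figure to reproduce. The check compares the schedule tables with the text and adds day arithmetic.

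**Step 1. The echocardiogram row in each schedule.**

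| Schedule | Marked at | Early Withdrawal cell |
|---|---|---|
| Table 1 (Cohort 1) | Screening, Visits 19 and 20 | Marked |
| Table 2 (Cohorts 2 and 3) | Screening, Visits 11 and 12 | Blank |
| Table 3.1 (Cohort 1 extension) | Visit 27 | Marked |
| Table 3.2 (Cohort 2 extension) | Visit 22 | Marked |
| Table 3.3 (Cohort 3 extension) | Visits 15 and 18 | Marked |

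**Step 2. The Section 6.15 list against Table 2's Early Withdrawal column.** The list has 26 items. Of these, 25 are marked in the column, and the echocardiogram is the one that is not. In the other direction, weight is marked in the table but absent from the list; it is still collected, because the Schedule marks it.

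**Step 3. Omission or choice?** In Table 2 the echocardiogram is the only assessment marked at both follow-up visits (11 and 12) and blank at Early Withdrawal. Burden does not explain this, since the same column calls for two kinds of MRI, DXA and a biopsy. Dose does not explain it either: Cohorts 2 and 3 start at 20 and 40 mg/kg, Cohort 1 at 5 mg/kg. Where Section 6.15 means to drop tests in the extension, it names them. An omission is the better reading.

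**Step 4. The exposed window.** Sections 6.3 to 6.7, which cover the dosing visits, contain no echocardiogram. Doses fall on Days 1, 29, 57, 85, 113, 141, 169 and 197, which is 8 doses. The first scheduled post-dose echocardiogram in Cohorts 2 and 3 is at Visit 11, Day 225. The window is 225 − 1 = 224 days, and 224 / 7 = 32 weeks. A subject leaving within it has had 1 to 8 doses.

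**Step 5. Effect of the blank.** For a dosed subject who leaves in that window and attends a final visit, scheduled post-dose echocardiograms number 0 under Table 2 as printed and 1 with the cell marked. Someone leaving between Visits 11 and 12 already has the Day 225 value.

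**Step 6. Scale.** Table 2 governs 8 + 8 = 16 of 20 planned subjects. One missing subject is 1/8 = 12.5% of a cohort's shift table and 1/20 = 5% of the total. These fractions would apply to any single missing value. They describe small cohorts and are not a forecast.

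**The case against.** The strongest objection is that the protocol already provides for the test. Section 6.15 names it, Section 6.14 allows it at an unscheduled visit on the investigator's or sponsor's decision, and Section 6.15 has the investigator request a final visit where applicable. The whole Section 6.15 list is permissive, so no main-period Early Withdrawal assessment is firmly required there. This stands as a limit on severity. It does not remove the inconsistency, because the text refers the site to a table that omits the test.

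A second objection is that the point rests on one empty cell, and text extracted from a PDF can lose a mark. Table 1 has an example: its adverse event monitoring row has cells run together and blanks at visits where Sections 6.4 to 6.8 require that monitoring. The Table 2 echocardiogram row shows no such merging, keeps all 13 visit cells, and sits beside ECG and laboratory rows that retain their Early Withdrawal marks. A true blank is more likely, but it should be confirmed on the page.

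A reader might go further and infer that anyone leaving before Day 225 goes without an LVEF, or that the referral rule cannot be applied. The documents do not support either. Subjects who only stop treatment stay in follow-up and keep Days 225 and 337. Those who leave the study and also withdraw consent to further disclosure have no further evaluations under any schedule, and those who do not attend gain nothing from the mark. Where a final visit does take place, an echocardiogram may still be done. ECG and troponin I are marked at Early Withdrawal in Table 2, and Section 1.12.4 calls the cardiac risk hypothetical and sets no cardiac stopping rule.

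**Conclusion.** The inconsistency is real and minor. As printed, Table 2 schedules no post-dose LVEF or LVESV for a dosed Cohort 2 or 3 subject who leaves the study entirely before Visit 11 and attends a final visit. For that subject the Section 7.10 comparison is unscheduled, though still permitted.

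The size is one cell and, per affected subject, one echocardiogram instead of none. The 16 subjects under Table 2 should not be read as the number affected: the documents give no withdrawal rate, and the group defined above is likely to be small. No formal test is affected, since LVEF is only summarised descriptively. Nor does the blank cell create the long interval between the screening and Day 225 echocardiograms for subjects who remain. That interval is the planned schedule, and the correction would leave it unchanged.

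The conclusion assumes that the blank is in the source PDF and that sites schedule from the table, as Sections 6.15 and 7.1.5 direct.

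**What to change.** Confirm the blank in the source PDF, then mark the echocardiogram in the Early Withdrawal column of Table 2, as in Table 1 and Tables 3.1 to 3.3. Section 6.15 and the SAP need no change. The cost is one table cell and at most one echocardiogram, already listed in Section 6.15, per full withdrawal before Visit 11 with a final visit.
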